## **Arm 2: Ranibizumab + Grid&Direct short pulse laser photocoagulation**

Patients will start study treatment with ranibizumab on Baseline (Day 1) and having reached stable status (i.e., satisfied stabilization criteria as per [Section 5.5.4.2](#)), ranibizumab treatment may be temporarily discontinued. Patients should be monitored monthly for VA and disease activity. Ranibizumab injections are given using PRN regimen i.e., according to the Japanese label of ranibizumab. The minimum gap required between 2 injections of ranibizumab will be  $30 \pm 7$  days.

Grid&Direct short pulse laser photocoagulation treatment must be applied to the target within vascular arcades as soon as indicated. If in the investigator's opinion dense macular hemorrhage and/or severe retinal edema preclude laser treatment, laser photocoagulation should be postponed until resolution of the hemorrhage permits laser treatment. The criteria for PRN of Grid&Direct short pulse laser photocoagulation is defined in [laser operation manual](#) in detail.

Following the complete application of the initial laser treatment, further laser treatment can be applied in the presence of ME due to BRVO at the investigator's discretion at minimal intervals of  $30 \pm 7$  days.

Laser photocoagulation will be optional if BCVA is greater than or equal to 0.8 in decimal VA which is equivalent to 0.12 units in logMAR (or 79 letters in ETDRS) or in the absence of ME.

### **5.5.4.2 PRN (re-treatment/stabilization) criteria**

The PRN criteria for ranibizumab treatment is as detailed below:

After Baseline (Day 1) visit, if any one or more criteria from the below list is met, the patient should be considered for ranibizumab treatment (**re-treatment criteria**)

1. Center subfield thickness  $\geq 300 \mu\text{m}$
  2. An increase of CSFT  $\geq 20\%$  compare to minimum value during the treatment period
  3. The loss of VA due to disease activity secondary to BRVO (disease activity includes macular edema (ME), intra-retinal cysts, sub-retinal fluid, macular hemorrhage etc.). This criteria is based on Investigator's judgement including the following scenarios:
    - a. The VA is expected to improve if the existing disease activity is removed, hence investigator decides to treat with ranibizumab
    - b. The VA is expected to be decreasing because of the existing disease activity, hence investigator decides to treat with ranibizumab
    - c. The VA has decreased as compared to the previous month because of the appearance of disease activity, hence investigator decides to treat with ranibizumab (This criterion is to restart ranibizumab after interruption)
- If all the above criteria are not satisfied, then the patient should not be treated with ranibizumab (**stabilization criteria**), i.e.,
    1. Center subfield thickness  $< 300 \mu\text{m}$

2. An increase of CSFT < 20% compare to minimum value during the treatment period
3. VA is stable and the disease activity is in the state of not affecting VA (based on investigator's judgement).

#### **5.5.4.3 Treatment of the fellow eye**

Patients who develop visual impairment due to ME secondary to RVO in the fellow eye (non-study eye) during the study that, in the investigator's opinion, qualifies for and requires treatment, may be treated at the investigator's discretion according to the standard treatment, including administration of ranibizumab. Ranibizumab will be injected in accordance with the rule of usual care and should be applied as per Japanese label.

Treatments of the fellow eye with ranibizumab should not be performed on the same day as treatments with ranibizumab of the study eye. Treatment of the fellow eye must be scheduled in a way not to disturb the schedule for visits and treatments of the study eye. Treatment will be captured on the eCRF. The fellow treated eye must be monitored according to routine practice and AE(s) and serious adverse events (SAEs) are captured on eCRFs. If fellow eye is treated with ranibizumab, examinations will be same as study eye.

Treatment with other anti-VEGF medication (e.g., pegaptanib (Macugen®), bevacizumab (Avastin®), aflibercept (EYLEA®)) and intra- or periocular corticosteroids (including sub-Tenon) are prohibited.

Treatment with ranibizumab for non-RVO indications in the fellow eye will be permitted in the same rule with RVO in the fellow eye within the limits of Japanese package insert, but the other anti-VEGF medication is prohibited.

#### **5.5.5 Permitted dose adjustments and interruptions of study treatment**

Dose adjustments, i.e., adjustments of the injection volume of ranibizumab dose solution, are not permitted.

Adjustments of the PRN dosing regimen of ranibizumab that is described as part of the study treatment administration in [Section 3.1](#) and [Section 5.5.4](#) are not permitted.

Ranibizumab treatment should be withheld and treatment should not be resumed earlier than the next scheduled treatment in the event of:

- A decrease in BCVA of  $\geq 0.6$  units in logMAR compared with the last assessment of VA,
- An IOP of  $\geq 30$  mm Hg,
- A retinal break,
- Performed or planned intraocular surgery within the previous or next 28 days.

Laser photocoagulation should be withheld and treatment should not be resumed earlier than the next scheduled treatment in the event of:

- A significant increase in macular ischemia as judged by the investigator,
- Absence of macular edema,
- Dense macular hemorrhage.

These changes must be recorded on the Dosage Administration Record eCRF.

### 5.5.6 Rescue medication

Rescue medication will not be permitted in this study.

### 5.5.7 Concomitant medication

The investigator should instruct the patient to notify the study site about any relevant prior medications (especially those related to ocular treatment) and any medications he or she takes preceding Baseline (Day 1) (once the informed consent is signed) until the conclusion of the study participation. Any relevant medications and significant non-drug therapies administered preceding Baseline (Day 1) before start of study treatment will be listed on Prior medication therapy page of eCRF and all medications and significant non-drug therapies (including physical therapy and blood transfusions) administered after the patient starts treatment must be listed on the concomitant medications/significant non-drug therapies eCRF.

Protocol specific medications (e.g., dilating drops, fluorescein dyes) and pre- and post-injection medications (e.g., topical anesthetics, topical antimicrobials) used by a patient during the study are not considered concomitant medications although these are listed in eCRF if used.

### 5.5.8 Prohibited medication

The following treatments are not allowed in the study eye throughout the entire study:

- Pan retinal and sector laser photocoagulation on the outside of vascular arcade or any other type of intervention for RVO (e.g. vitrectomy, optic neurotomy, sheathotomy, filtration surgery).
- Any type of intraocular surgery including cataract surgery.
- Intra-/peri-ocular corticosteroids (including sub-Tenon, but excluding topical formulations of any drug) and intra-ocular corticosteroid implants (e.g. dexamethasone (Ozurdex®), fluocinolone acetonide (Iluvien®)).

**The use of the following medications is not allowed in both eyes throughout the entire study:**

- Non-study anti-angiogenic drugs (including any anti-VEGF drugs) (e.g. pegaptanib (Macugen®), bevacizumab (Avastin®), and aflibercept (EYLEA®)).

**The following systemic medications are not allowed throughout the entire study:**

- Corticosteroids,
- Anti-VEGF drugs (e.g. sorafenib (Nexavar®), sunitinib (Sutent®), bevacizumab (Avastin®) and ziv-aflibercept (ZALTRAP®)),
- Medications known to be toxic to the lens, retina or optic nerve including deferoxamine, chloroquine/hydroxychloroquine (Plaquenil), tamoxifen, phenothiazines other than temporary use with common cold and upper respiratory infection (i.e., exclude PL granules), and ethambutol.

Furthermore, any type of investigational drug or investigational intervention (e.g. isovolumic hemodilution, intravitreal tissue plasminogen activator (TPA)) is prohibited throughout the study.

Prohibited treatments are summarized in [Table 5-1](#).

**Table 5-1 Prohibited treatment**

Medication	Action to be taken
Other anti-VEGF drugs (ocular or systemic)	Discontinue study treatment and study
Pan-retinal laser photocoagulation – study eye	Discontinue study treatment and study
Intra-/peri-ocular corticosteroids (including sub-Tenon) – study eye	Discontinue study treatment and study
Intra-ocular corticosteroid implants – study eye	Discontinue study treatment and study
Systemic corticosteroids	Discontinue study treatment
Intraocular surgery – study eye	Discontinue study treatment and study
Deferoxamine	Discontinue study treatment
Chloroquine/hydroxychloroquine	Discontinue study treatment
Tamoxifen	Discontinue study treatment
Phenothiazines other than temporary use with a common cold and an upper respiratory infection	Discontinue study treatment
Ethambutol	Discontinue study treatment
Investigational drugs and interventions	Discontinue study treatment

### **5.5.9 Emergency breaking of assigned treatment code**

Not applicable.

## **5.6 Study completion and discontinuation**

### **5.6.1 Study completion and post-study treatment**

Patients who successfully complete the study through Month 12 will be considered to have completed the study.

No extension to this study has been planned.

### **5.6.2 Discontinuation of study treatment**

Patients can discontinue treatment because of the appearance of a new health condition suspected to require appropriate care or require medications prohibited by the protocol ([Section 5.5.8](#)), unacceptable AEs, refusal to continue treatment, or at the investigator's discretion based on his/her clinical judgment.

Study treatment *must* be discontinued under the following circumstances:

- Emergence of the following AEs:
  - Rhegmatogenous retinal detachment
  - Stage 3 or 4 macular hole
  - Stroke or transient ischemic attack (TIA)
- Pregnancy
- Use of prohibited treatment as per [Table 5-1](#).
- Any other protocol deviation that results in a significant risk to the patient's safety.

The reason for study treatment discontinuation will be recorded on the Treatment Period Completion eCRF.

Patients who permanently discontinue study treatment and start certain prohibited treatments (see [Table 5-1](#)) should be withdrawn from the study and undergo all assessments for the Visit 14 (End of study (EOS)) as described in [Table 6-1](#).

Patients who discontinue study treatment and do not start a prohibited medication per [Table 5-1](#) should NOT be considered withdrawn from the study and continue their scheduled follow-up assessments until Visit 14 (EOS). A Study Treatment Period Completion eCRF should be completed, giving the date and primary reason for stopping study treatment.

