### 5.5.4.1 Treatment Period (Day 1 to Month 11)

#### Arm 1: Ranibizumab monotherapy

Patients will start study treatment with ranibizumab on Baseline (Day 1) and having reached stable status (i.e., satisfied stabilization criteria as per [Section 5.5.4.2](#)) ranibizumab treatment may be temporarily discontinued. Patients should be monitored monthly for VA and disease activity. Ranibizumab injections are given using PRN regimen i.e., according to the Japanese label of ranibizumab. The minimum gap required between 2 injections of ranibizumab will be  $30 \pm 7$  days.

If there is no improvement in VA [REDACTED] imaging over the course of the first 3 injections, continued treatment is not recommended and the patient may receive alternative treatment at the investigator's discretion (for consequences refer to [Section 5.6.2](#)).

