### **9 Data analysis**

The statistical analysis will be performed by Product Lifecycle Services (PLS) of Novartis.

The primary objective is to demonstrate that PRN regimen of 0.5 mg ranibizumab with Grid&Direct short pulse laser photocoagulation reduces the burden of frequent ranibizumab injections as compared to ranibizumab monotherapy.

The primary objective will be assessed by the mean number of ranibizumab injections applied up to Month 11.

Summary statistics for continuous variables will generally include the number of patients (N), minimum, lower quartile, mean, median, upper quartile, and maximum. For categorical or binary variables, the number and percent of patients in each category will be presented. P-values presented will be 2-sided unless otherwise specified.

Data analyses will be presented at all time points assessed, by treatment group including graphical presentations, where appropriate. For statistical analysis purpose, baseline values will be considered to be the last available values collected before Day 1. Day 1 will be defined for statistical analysis purpose as the time point of first treatment (associated to baseline visit).

For patients who receive a prohibited medication for the study indication in the study eye, the efficacy data will be excluded from the per-protocol efficacy analysis.

Further details will be provided in the statistical analysis plan (SAP).

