#### **9.1 Analysis sets**

The **Randomized Set** will consist of all randomized patients.

**The Full Analysis Set (FAS)** will consist of all randomized patients who received at least one administration of ranibizumab injection. In case there are safety concerns after administration of laser photocoagulation at Baseline (Day 1) and ranibizumab injection is not given during the entire study, the patient will still be included in the FAS, as there was an intention to treat

the patient with ranibizumab. Following the intent-to-treat principle, patients will be evaluated according to the treatment assigned to at randomization.

No data will be excluded from the FAS analyses because of protocol deviations.

**The Per Protocol Set (PPS)** will consist of all patients in the FAS who received at-least the first mandatory administration of ranibizumab injection and have at least one post-baseline assessment for BCVA and have no clinically significant protocol deviations.

Clinically significant protocol deviations will be defined in the Statistical Analysis Plan. The criteria and determination of clinically relevant protocol deviations and patient specific identification of data to be excluded from the PPS will be databased and finalized prior to database lock.

The **Safety Set** will consist of all patients who received at least one administration of ranibizumab injection and had at least one post-baseline safety assessment. The statement that a patient had no AEs also constitutes a safety assessment. Patients will be evaluated according to treatment received.

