### **9.4.2 Statistical model, hypothesis, and method of analysis**

The primary analysis will be conducted at Month 12 within the FAS using observed data.

The following 1-sided hypothesis will be tested at the alpha level of 0.025:

$H_0: \mu_{\text{Ranibizumab-Laser}} - \mu_{\text{Ranibizumab-Mono}} = 0$  versus

$H_1: \mu_{\text{Ranibizumab-Laser}} - \mu_{\text{Ranibizumab-Mono}} \leq 0$

where  $\mu_{\text{Ranibizumab-Laser}}$  and  $\mu_{\text{Ranibizumab-Mono}}$  are the unknown mean values of the number of ranibizumab injections for the related treatment arms up to Month 11.

The statistical hypothesis testing of the number of ranibizumab treatments will be based on a stratified Cochran-Mantel-Haenszel (CMH) test. Stratification will be done based on categories of baseline decimal VA ( $<0.3$ , or  $\geq 0.3$ ). Difference of mean number of injections, 95% confidence interval (CI) of difference and one-sided p-value of the CMH test will be reported.

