#### **9.5.1.3 Handling of missing values/censoring/discontinuations**

For the secondary efficacy variables (BCVA, CSFT etc.), the analysis will follow a LOCF approach with the specification that missing values will be replaced by the last post baseline observation before the missing time point.

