## **9.8 Sample size calculation**

In order to detect a clinically meaningful difference in the number of injections (at least 2 injections) at Month 11, as suggested by the principal investigators, this study will randomize at least 56 patients (28 per arm).

For the sample size calculation, we will assume a difference between arms of 2 injections and a standard deviation (SD) of 2.32 (based on CAVNAV study (Liegler et al. 2014)). Based on the non-parametric Wilcoxon-Mann Whitney test for the difference in means this would require 25 patients per arm with 80% power and a 0.025 significance level (1sided), however assuming approximate 10% drops out rate, a total of at least 56 patients (28 per arm) are required to be randomized.

Approximately 70 patients will need to be screened in order to have at least 56 patients eligible and commencing treatment in the trial.

All sample size calculations performed using EAST 6.0.

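### Patients who start one of five prohibited treatments are taken out of the study as well as off treatment, so their later vision, retinal thickness and anti-VEGF use go unobserved although they could still be followed

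*Protocol*

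**What the plan says.** Protocol Section 5.6.2 requires study treatment to stop on any Table 5-1 treatment. It then separates two groups. Patients who start certain listed treatments "should be withdrawn from the study and undergo all assessments for the Visit 14 (End of study (EOS" visit. Patients who stop without starting a listed treatment are not withdrawn and keep their scheduled assessments to Visit 14.

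Table 5-1 gives the action "Discontinue study treatment and study" in five of twelve rows: other anti-VEGF drugs (ocular or systemic) and, for the study eye, panretinal laser, intra-/periocular steroid, steroid implant and intraocular surgery. The other seven rows stop treatment only.

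Section 5.5.4.1, under Arm 1 only, says that without improvement over the first three injections "continued treatment is not recommended and the patient may receive alternative treatment at the" investigator's discretion, and refers to 5.6.2 for the consequences.

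Footnote p of Table 6-1 places the end-of-study visit of a patient who leaves early 30 (+7) days after the last treatment or visit. For BCVA and CSFT, Section 9.5.1.3 states that "missing values will be replaced by the last post baseline observation before the missing time point". Section 9.4.3 takes the primary count as the injections given during the study, without imputation.

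Section 9.1 invokes the intent-to-treat principle for the FAS and adds: "No data will be excluded from the FAS analyses because of protocol deviations". For prohibited medication given for the study indication in the study eye, Section 9 says "the efficacy data will be excluded from the per-protocol efficacy analysis".

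**The concern.** The patients in the five rows have neither withdrawn consent (5.6.3) nor been lost (5.6.4). The protocol itself ends their observation, and some of these exits depend on outcome. A patient who does not improve may be switched under 5.5.4.1. A retinal detachment or stage 3 or 4 macular hole stops only treatment under 5.6.2, but surgical repair then brings in the intraocular surgery row and ends the study for that patient.

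Section 1.1 states the aim as fewer injections with no loss of efficacy or safety. For these patients the efficacy half would rest on a value from near the time of failure. The planned sensitivity analyses (9.4.4, 9.5.1.4) use the per-protocol set and cannot recover them. An analysis plan cannot analyse values that were never collected.

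The primary endpoint has a related problem. A patient moved to another anti-VEGF drug stops adding ranibizumab injections and so counts as having needed few. After study exit, nothing in the data shows whether that low count reflects less need or a different drug.

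**Working it through.** **1. The plan's own figure.** Section 9.8: "we will assume a difference between arms of 2 injections and a standard deviation (SD) of 2.32", with 80% power, one-sided 0.025 and the Wilcoxon-Mann-Whitney test. By Noether's formula, p = Φ(2 / (2.32 × √2)) = 0.7289, and n per arm = (1.960 + 0.842)² / [6 × (0.7289 − 0.5)²] = 24.96, so 25. With 10% dropout, 25 / 0.90 = 27.8, so 28 per arm and 56 in total. The sample size reproduces and is not in question; 28 is used as the denominator below.

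**2. What exit does to one patient's BCVA and CSFT.** The average change in 9.5.1.1 is the mean of 12 monthly changes. After a last regular visit at Month m, the number carried forward is 12 − m, or 11 − m if the early end-of-study value is used as Month m + 1.

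- m = 1: 11 or 10 of 12
- m = 3: 9 (75%) or 8 (67%) of 12
- m = 6: 6 or 5 of 12
- m = 9: 3 or 2 of 12

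The Month 12 value is unobserved in every one of these cases. For m = 3 (Day 90), the early visit falls at Day 120 to 127, which is 233 to 240 days before Day 360.

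**3. Share of one arm.** The protocol gives no exit rate, so assume 1 to 3 exits after Month 3 among 28 FAS patients. The unobserved share of Month 12 values is 1/28 to 3/28 = 3.6% to 10.7%. The share of all monthly values carried forward runs from 8 / (28 × 12) = 2.4% (one exit) to 27 / (28 × 12) = 8.0% (three exits, 9 values each). The share is small, but it is not a random sample of the arm.

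**4. What freezes the injection count.** Two rules act at the same moment. The requirement to stop study treatment on any Table 5-1 treatment ends ranibizumab. The study-exit rule ends recording. Removing the second leaves the first, so the primary count would be the same. What exit removes is knowledge of later anti-VEGF treatment.

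**5. How far an all-agent count could differ.** There are at most 12 monthly injections (Day 1 and Months 1 to 11). A patient switched after three has up to 12 − 3 = 9 monthly slots left. If x further injections of another agent are given, the all-agent arm mean exceeds the ranibizumab mean by x/28 per such patient: 0 for x = 0, and 9/28 = 0.32 for x = 9. Three more switches in one arm than in the other would separate the two analyses by 0 to 27/28 = 0.96 injections, against the planned difference of 2. Equal numbers in both arms largely cancel. Both x and the number of switches are assumptions.

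**The case against.** Several objections are sound and limit the point.

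- **Power and type I error.** A reader might infer that the exit rule costs power or inflates the one-sided error of the primary test. The documents do not support that. The count freezes because study treatment stops, and the primary test would be the same if these patients stayed in follow-up. Nor is there a basis for supposing that a non-responder would otherwise have had many more ranibizumab injections, since 5.5.4.1 advises against continuing.
- **Section 9.1.** A reader might say that it is contradicted. It is not. It fixes the arm in which patients are analysed and forbids excluding collected data, and these patients remain in the FAS. The poor fit is with the principle it invokes.
- **Complications.** A reader might infer that serious complications go unrecorded. Section 7.1 requires adverse events to be followed to resolution or until judged permanent, and 7.2.2 extends serious-event reporting by 30 days. What is lost is scheduled BCVA and CSFT.
- **Nature of the exits.** Not all exits reflect failure. The anti-VEGF row includes systemic and fellow-eye use, and 5.5.8 counts cataract surgery as intraocular surgery.
- **Direction.** The failure route is printed for Arm 1 only. Early switches there lower the monotherapy count and work against the superiority claim; switches in Arm 2 would favour it.
- **Weight.** BCVA and CSFT are secondary, to be evaluated (2.2), and no non-inferiority test is planned.

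None of this explains why consenting patients should lose their remaining visits. Other treatment stoppers keep theirs, and Section 9 already removes the efficacy data of patients given prohibited medication for the study indication from the per-protocol analysis.

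**Conclusion.** The point holds as a cheap improvement. Five rows of Table 5-1, through 5.6.2, end observation for patients who could be followed, and some of those exits depend on outcome. Their Month 12 BCVA and CSFT are not observed. An exit after Month 3 leaves 8 or 9 of 12 monthly values carried forward, depending on whether the early end-of-study value is assigned to Month 4. With one to three such exits in an arm of 28 (assumed), 3.6% to 10.7% of that arm's Month 12 values are affected. The FAS comparison bearing on no loss of efficacy is weakened to that extent, in a direction that cannot be known in advance.

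Separately, the frozen ranibizumab count can make a switch look like low need. Study exit does not cause this, but it prevents the data from showing it. No power or error figure should be attached to the exit rule.

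**What to change.** Leave all rules on stopping study treatment unchanged, and separate them from the end of observation.

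1. In the five rows of Table 5-1, change the action to: *stop study treatment; continue scheduled follow-up to Month 12 unless consent is withdrawn*.
2. Rewrite both closing paragraphs of 5.6.2 so that every patient who stops study treatment, including one who starts any Table 5-1 treatment, continues to Visit 14. Deleting the withdrawal sentence alone is not enough, because the next paragraph grants follow-up only to patients who start no listed treatment. The rewrite also settles the seven rows that stop treatment only, which that wording does not clearly cover. Keep the early end-of-study visit for patients who do leave, and align the cross-reference in 5.6.5.
3. Record in the eCRF every later study-eye anti-VEGF injection (any agent), steroid, laser and surgery.
4. Use the observed BCVA and CSFT after the switch in the FAS. Keep the Section 9 exclusion from the per-protocol analysis.
5. Add a supportive analysis of all study-eye anti-VEGF injections up to Month 11, whatever the agent.

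The cost is a short amendment and the remaining scheduled visits of a few patients. FAS efficacy will then include the effect of later treatment, as the intent-to-treat principle implies. Patients already withdrawn may not be recoverable: Amendment 2 reports 59 randomized by 21 January 2018.
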